Effect of PVP-I Nasal Sprays vs Normal Saline Nasal Sprays on
SARS-CoV-2 Nasopharyngeal Titers

NCT04347954

Document Date: July 10, 2020

Background Summary

Human transmission of SARS-CoV-2 (COVID-19) occurs primarily through droplet spread into the nose and mouth. Arresting COVID-19 replication after infection of the nasal tissues specifically would decrease the duration and severity of infection in COVID-19-exposed patients, and may significantly impact COVID human to human transmission. Povidone-iodine (PVP-I) solution is a widely available, inexpensive antiseptic medication, used in the surgical theater to reduce the incidence of surgical wounds and intranasally to reduce MRSA colonization. However, the role of PVP-I in the treatment of nasal infections is limited. Interestingly, prior in vitro studies have demonstrated dilute PVP-I solutions, in concentrations as low at 0.23%, produce a ≥ 4 log10 decrease (inactivation of $\geq 99.99\%$) in SARS and MERS virus titers within 15 seconds.^{1,2} Both viruses share high structural overlap with COVID-19. A study of 29 patients with recalcitrant sinusitis found reduced bacterial growth with good safety profile after use of 0.08% PVP-I nasal rinses.³ PVP-I nasal sprays of up to 4.4% concentration have also been used on healthy volunteers without adverse effects or nasal tissue damage.⁴ In Wuhan, China, PVP-I was recently used empirically by healthcare providers devoid of COVID-19 protection, given its ease of use, and potential for mitigating infection. Given this encouraging background, and current world events, we propose testing dilute PVP-I sprays as a topical treatment to directly ablate COVID infection within the nasal cavity.

Specific aims

1. To determine if PVP-I nasal sprays reduce viral shedding in the nasopharynx and nasal cavity
 - a. Hypothesis 1: PVP-I nasal sprays will reduce viral shedding in the nasopharynx and nasal cavity as determined by PCR testing when compared to control groups
2. To determine if PVP-I nasal sprays affect the severity and time to resolution of signs and symptoms of COVID-19
 - a. Hypothesis 2a: PVP-I nasal sprays will not change the severity or time to resolution of systemic signs and symptoms (such as fever, fatigue) when compared to control groups
 - b. Hypothesis 2b: PVP-I nasal sprays will reduce the duration of anosmia symptoms when compared to control groups
3. To determine adverse effects of PVP-I nasal sprays

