 - a. Hypothesis 3: PVP-I nasal sprays will not be associated with a greater rate of adverse effects as compared to the control groups

Methods

Overview of study design

This is a prospective, double-blind, placebo controlled, randomized control trial of COVID-19 positive patients that has three study arms.

Arms:

- (1) 2% povidone iodine nasal spray – two sprays to each nare four times a day for 5 days
- (2) 0.5% povidone iodine nasal spray – two sprays to each nare four times a day for 5 days
- (3) Control – Dyed normal saline (0.9% NaCl) spray – two sprays to each nare four times a day for 5 days

Study population: COVID-19 positive inpatients and outpatients

Inclusion criteria:

1. ≥ 18 years ago
2. Diagnosis of COVID-19 by lab test within 5 days of study participation

Exclusion criteria:

1. Allergy to "iodine," shellfish, or food dye
2. Receiving intranasal steroids
3. Sinus surgery within 30 days of beginning the study
4. Intubated at the time of enrollment
5. Pregnancy
6. Participation in other COVID-19 studies - to be determined on a case by case basis

Measurements/Outcomes

The primary outcome measure is the viral load on nasopharyngeal swab determined by quantitative PCR testing. A baseline sample (Day 1) will be obtained prior to first administration of the sprays. Subsequent samples will be collected at 4 hours after first administration and on day 5 after initiating nasal sprays.

Intake questionnaire – dates of symptom onset, comorbid conditions, specific questions regarding taste and smell disturbances

Patient reported symptoms (completed on Day 3 and Day 5) – fever, fatigue, change or loss of sense of smell, change or loss of sense of taste, nasal congestion, sore throat, etc

Adverse effects questionnaire (completed on Day 3 and 5) – Nasal burning/pain, headaches, ear pain, sneezing, nose bleeds, rash

University of Pennsylvania Smell Identification Test (completed on day 1 and day 30) – to assess smell recovery in COVID-19 patients

Statistics

T-test or ANOVA to compare difference in mean viral load between groups. Chi-square to assess for differences in signs, symptoms, adverse effects.

Sample size: 45 subjects (15 subjects per study arm)

Study Procedures - Outpatient

Recruitment strategy

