We have also received approval from [name] who is the Operations Manager of the Galvez research lot to utilize the tent space or the parking lot space at this site for study procedures. Weekday study procedures will take place at this site ([name]).

Participants will complete the first questionnaire and take the University of Pennsylvania Smell Identification Test (UPSIT) on the day of enrollment. This is a multiple-choice scratch and sniff test that is self-administered. A baseline nasopharyngeal sample will be taken. Next the first dose of the nasal spray will be given. Subjects will have the option to stay or return for the four hour sample collection timepoint. Four hours later, a member of the research team will obtain the 4-hour post-administration nasal sample. Subjects will then return home. Participants will be given (physical or electronic) a gift card for \$25 at the end of the day.

Participants will continue to self-administer the spray as instructed while at home. They will also take daily symptom questionnaires administered through REDCap. Participants will return for a drive-through nasal swab at [name] or at the Galvez lot on Day 5.

On day 30, participants will complete an UPSIT, self-administered smell test, which will be given to patients with a self-addressed, pre-paid envelope to return.

Close Out

The study medication will be discontinued on Day 5. The second gift card (\$25) will be mailed either through the postal service or through email to participants approximately 30 days after the first study visit upon completion of the final UPSIT.

Specimen Handling

Each sample will be labelled with a subject's unique record ID number. These samples will be processed in the Stanford clinical virology lab (permission has been obtained from [name]) and results associated with a given record ID number in REDCap.

Payment/Reimbursement

Participants will be given a total of \$50 in gift cards if they complete the study. They will receive a \$25 gift card at the end of the first in person study visit. If they complete the remaining in person visits on Days 5, they will be mailed (either via postal service or email) the second \$25 gift card along with the final smell test.

Safety of proposed treatment arms

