A small quantity of food dye is commonly used on mucosa membranes in the head and neck in routine clinical practice for instance to assess for fistula or to assess swallow function.⁵ It has also been used in numerous prior research studies assessing the distribution of drug delivery methods in the nasal cavity.⁶ There is no added risk to including this in the control group saline solution.

PVP-I solutions are routinely used as mouth washes with minimal absorption through the mucus membranes.⁷ Additionally, iodine solutions are used in the nose for MRSA decolonization and have been used long term in nursing home residents.⁸ Furthermore, prior studies have used concentrations as high as 4.4% in nasal spray form for extended periods in healthy volunteers without adverse effects.⁴ In our clinical practice, 10% PVP-I is used in the mouth and nose as a surgical prep prior to procedures in the operating room. Additionally, some of our patients with chronic sinus disease have been instructed to use high volume (240 mL) nasal rinses of PVP-I for several months without observed adverse effects or objective changes on nasal endoscopy.

With long term use of iodine containing compounds, there is a theoretical risk of excessive iodine absorption which could affect the thyroid gland. However, given the short duration of our study, the cumulative exposure will remain far lower than in many common medical procedures.

0.5% PVP-I contains 5 mg/mL and 2% PVP-I contains 20 mg/mL. The estimated volume delivered by two nasal sprays to each nare in a single administration is 0.33 mL.⁹

0.33 mL/dose x 4 doses/day x 7 days = 37.2 mL of solution administered.

At a 0.5% PVP-I concentration, the total amount of iodine administered is 186 milligrams. At 2.0% PVP-I, the total amount of iodine administered is 744 milligrams or 0.744 grams. The most common medical procedure in which patients are exposed to iodine are computed tomography (CT) scans which use iodinated contrast. The average dose per scan is estimated to be 15-37 grams of iodine¹⁰ which is an order of magnitude greater exposure to iodine than what is proposed in this study.

Participant study timeline

Day 0	Enrollment, intake questionnaire, baseline NP swab, first dose of sprays, 4-hour post NP swab, UPSIT
Day 1	Continue sprays
Day 2	Continue sprays, symptom questionnaire, adverse symptoms and compliance questionnaire
Day 3	Continue sprays, daily questionnaire

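### Aim 2 asks about severity, time to resolution and duration of symptoms, but the only stated test is a chi-square with no unit of analysis for the repeated forms

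*Combined protocol and SAP*

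**What the plan says.** The Statistics paragraph under Methods has two sentences on testing. The first, "T-test or ANOVA to compare difference in mean viral load between groups", concerns viral load only. The second covers everything else: "Chi-square to assess for differences in signs, symptoms, adverse effects". It names no day, unit of analysis or rule for combining a participant's forms.

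The second aim under Specific aims is "To determine if PVP-I nasal sprays affect the severity and time to resolution of signs and symptoms of COVID-19". Its hypotheses concern severity and time to resolution of systemic symptoms (2a) and duration of anosmia (2b).

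The number of symptom forms per participant differs by section:

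- **Measurements/Outcomes:** two forms, "Patient reported symptoms (completed on Day 3 and Day 5").
- **Study Procedures – Outpatient, Active Phase:** "They will also take daily symptom questionnaires administered through REDCap".
- **Participant study timeline:** three forms. Day 2 reads "Continue sprays, symptom questionnaire, adverse symptoms and compliance questionnaire", Day 3 reads "Continue sprays, daily questionnaire", and Day 4 has a further daily questionnaire.

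Adverse-effect forms are completed twice in both Measurements/Outcomes and the timeline. The sample size is "Sample size: 45 subjects (15 subjects per study arm").

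**The concern.** The outcome named in Aim 2 and the named test do not match. A participant who loses a symptom after one day and one who keeps it throughout give the same answer on an ever/never table. On a last-form table, the day of resolution is lost. Neither table measures duration or time to resolution, and a grade of severity would have to be cut to yes/no first.

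The missing unit of analysis is a second gap. A Pearson chi-square assumes independent responses, and several forms from one person are not independent. As written, the plan permits a table of participants, a table of one chosen day or a table of all forms, and the choice could be made after the data are seen. Two of the three stated aims (symptoms and adverse effects) rest on this one sentence.

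**Working it through.** **The plan's own figure.** 3 arms × 15 = 45. No alpha, power, effect size or event rate is given, so there is nothing further to reproduce.

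**Inputs.** From the documents: 15 per arm, three arms, and m = 2 forms (Measurements/Outcomes), 3 (timeline) or daily (Active Phase). Assumed: m = 4 for daily forms, two-sided alpha 0.05, and within-person correlation ρ = 0.3 to 0.7.

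**Step 1: error rate if all forms were pooled as independent.** The design effect is DE = 1 + (m − 1)ρ, and the true rejection rate is about P(χ² > critical value / DE). With three arms (2 df) this simplifies to 0.05^(1/DE). With two arms (1 df) it is P(χ²₁ > 3.841/DE).

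| Forms | DE (ρ 0.3 to 0.7) | Two arms, formula | Two arms, simulated | Three arms, formula | Three arms, simulated |
|---|---|---|---|---|---|
| 2 | 1.3 to 1.7 | 8.6–13.3% | 9–14% | 10–17% | 10–18% |
| 3 | 1.6 to 2.4 | 12–21% | 12–22% | 15–29% | 15–30% |
| 4 | 1.9 to 3.1 | 15.5–26.6% | 16–28% | 21–38% | 21–40% |

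Example: four forms, ρ = 0.7, three arms gives 0.05^(1/3.1) = 0.38. The simulations are beta-binomial with 15 per arm. At ρ = 0.7 the effective number per arm is 30/1.7 = 17.6 with two forms and 60/3.1 = 19.4 with four, although 30 and 60 forms would be counted.

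**Step 2: one answer per participant.** In the three-arm simulations, at event probabilities 0.2 and 0.4, an ever/never chi-square rejected about 5% of the time and a single-day chi-square 4–5%. Both are acceptable. The single-day test leaves out 1 − 1/m of the forms: 50% with two, 67% with three and 75% with four. The ever/never test uses every form but not its timing.

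**Step 3: power of a per-participant summary.** The comparison is two arms of 15 with a 30-point difference in daily prevalence (70% v 40%, or 60% v 30%). A last-form chi-square has 36–38% power, and an ever/never chi-square over four forms has 33–45%. A Wilcoxon test on the proportion of forms with the symptom, with prevalence constant over days, has:

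- two forms: about 41–51%
- three forms: about 44–60%
- four forms: about 45–67%

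Its size is close to 5%. The higher figures go with lower correlation. If symptoms instead resolve steadily, the rank test ranges from about 2 points above the last-form test to about 5 points below it.

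**Step 4: adverse effects.** The expected number of events per arm is 15 × the overall rate. It falls below 5 whenever that rate is under 5/15 = one third; at 20% it is 3. The chi-square approximation is then doubtful.

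**The case against.** The strongest reply is that a chi-square between arms ordinarily means participants by arm. On that reading the error rate holds and the Step 1 inflation never arises. This stands: nothing in the documents says forms will be pooled, and a reader who infers that the plan commits to an inflated false-positive rate goes beyond the text.

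A reader might also infer that a chi-square must either pool forms or throw most of them away. The documents do not support that. One ever/never answer per participant uses every form and suits the adverse-effect rate in Hypothesis 3. Even a single-day test drops only half the forms under the two-form schedule, and half of the adverse-effect forms under either schedule. It drops most only for symptoms under the three-form or daily schedule.

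Third, a reader might expect a rank test to add power in all cases. Step 3 shows that it does not. With two forms and correlation 0.7 the gain over ever/never is about 4 points, and under steady resolution there may be none.

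Fourth, a mixed model, GEE or time-to-event analysis would also be defensible, the documents do not say that symptoms are graded, and these are secondary outcomes. All of this is fair. None of it supplies a unit of analysis or makes a yes/no count a measure of duration.

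**Conclusion.** The point holds as a mismatch and an omission. The named test cannot express what Aim 2 asks, and the unit of analysis for repeated forms is undefined. It should be corrected before unblinding, but it does not touch the primary viral-load outcome.

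The Step 1 error rates are conditional on an analysis that the plan leaves open but does not state. They also rest on assumed correlations of 0.3–0.7 and, for the upper figures, on four forms. The firm benefit of the change is an analysis that answers Aim 2. Any power gain depends on prevalence being roughly constant over days. The power figures assume 15 analysed per arm, so they would be lower for a symptom that only some participants had at intake.

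**What to change.** In the Statistics paragraph:

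1. For each symptom, define one summary per participant: the proportion of completed post-dose forms on which it is present, among participants who had it at intake. Compare arms by Kruskal–Wallis (three arms) or Wilcoxon rank-sum (two arms), and state in advance which.
2. For each adverse effect, use one ever/never answer per participant, compared by Fisher's exact test.
3. State that forms are never pooled as separate observations.
4. Reconcile the form days in Measurements/Outcomes, Active Phase and the timeline. The timeline counts from Day 0 and the other sections from Day 1. Shifting by one day aligns the adverse-effect forms (Days 2 and 4 with Days 3 and 5), but it does not reconcile two, three and daily symptom forms.

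The change needs no new visits or participants. The intake form should be checked: the plan lists symptom-onset dates and taste and smell questions there, but does not say that every symptom is recorded.

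The downsides are modest. The day-by-day course is tabulated rather than tested, an effect that appears only late is somewhat diluted, and the summary measures duration only over the days with forms.

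### Aim 2 asks about symptom severity, but the plan defines no severity scale and names only a chi-square, which cannot use the order in graded answers

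*Combined protocol and SAP*

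**What the plan says.** Under Specific aims, Aim 2 is "To determine if PVP-I nasal sprays affect the severity and time to resolution of signs and symptoms of COVID-19". Hypothesis 2a expects no change in systemic symptoms, Hypothesis 2b expects shorter anosmia, and Hypothesis 3 expects no greater rate of adverse effects on PVP-I.

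The Overview of study design has three arms: "2% povidone iodine nasal spray", "0.5% povidone iodine nasal spray" and "Control – Dyed normal saline (0.9% NaCl) spray". They form an ordered series of 2%, 0.5% and 0% PVP-I, and the safety section gives the strengths as "0.5% PVP-I contains 5 mg/mL and 2% PVP-I contains 20 mg/mL".

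Measurements/Outcomes lists symptom items and adverse-effect items. It gives no response scale or number of levels for either.

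For these outcomes the Statistics section says only "Chi-square to assess for differences in signs, symptoms, adverse effects". It does not say whether the test compares three arms at once, pairs of arms, or pooled PVP-I with control. The size is "Sample size: 45 subjects (15 subjects per study arm)", with no alpha, power, effect size or event rates.

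**The concern.** Severity is an ordered quantity. A Pearson chi-square gives the same result however the columns none, mild, moderate and severe are arranged, so a consistent shift towards milder symptoms earns no more credit than an erratic pattern of the same size. If answers are yes/no instead, the chi-square is an ordinary choice, but the severity half of Aim 2 has no measurement behind it. The plan does not say which case applies, and either one leaves a gap.

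For adverse effects, the overall test also ignores the order of the arms. That matters less, because yes/no recording suits a hypothesis about a rate, and using the arm order has a price as well as a benefit.

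At 15 per arm these comparisons have little power to spare. Severity that was not graded when collected cannot be recovered later.

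**Working it through.** **The plan's own figure.** The 45 subjects cannot be reproduced, because no inputs are given. At an assumed two-sided 5% and 80% power, 15 per arm detects a pairwise difference of (1.96 + 0.84) × √(2/15) = 1.02 SD. For rates of 20% against 50%, pairwise power is about 40%.

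**Inputs.** From the documents: three arms, 15 each. Assumed: two-sided 5%, no dropout, and all severity distributions, odds ratios and event rates below.

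**Severity, one case by formula.** Take four equally likely levels in control and an odds ratio of 4 towards milder symptoms. The control cumulative odds of 1/3, 1 and 3 become 4/3, 4 and 12, so the treated levels are 57.1, 22.9, 12.3 and 7.7%.

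- Chi-square, two arms, 3 df: noncentrality = n × Σ(p − q)²/(p + q) = 15 × (0.1258 + 0.0010 + 0.0432 + 0.0916) = 15 × 0.2616 = 3.92. Power is about 35%.
- Wilcoxon: the chance that a treated patient is milder, with ties counted half, is 0.571 × 0.75 + 0.229 × 0.50 + 0.123 × 0.25 + 0.125 = 0.699. The tie-corrected variance is 31/(12 × 15²) × (1 − 0.094) = 0.0104, SD 0.102. Then (0.699 − 0.5)/0.102 = 1.95, and power is about Φ(1.95 − 1.96), or 50%.

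Simulation of the same case (40,000 trials) gives 34.3% and 52.0%, a gain of 18 points. With three arms and the middle arm at √4 = 2, chi-square gives 25.3% and Kruskal-Wallis 40.9%, a gain of 16.

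**Severity, range.** Control distributions of 20/30/30/20% and 30/35/25/10%, odds ratio 3 to 4, 1,000 runs per setting:

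| Comparison | Chi-square | Rank test |
|---|---|---|
| Two arms (Wilcoxon) | 20-33% | 33-52% |
| Three arms (Kruskal-Wallis) | 16-25% | 25-42% |

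The ends differ by 13 and 19 points for two arms and by 9 and 17 for three. The simulation error is about √(0.25 × 0.75/1000) = 1.4 points per figure, so the gain is roughly 10-19. Null rejection was 4-6% for all tests. With three levels and an odds ratio of 2, the gain is only 10.3% to 12.9%. With five equal levels, an odds ratio of 5 and both strengths equally effective, it is 39.5% to 67.7%.

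**Adverse effects.** Let p̄ be the mean rate. The overall test (2 df) has noncentrality 15 × Σ(pᵢ − p̄)²/[p̄(1 − p̄)]. The Cochran-Armitage test with scores 0, 1, 2 (1 df) has 15 × (p₂% − p_saline)²/[2p̄(1 − p̄)]. With equal arms and equal spacing, the 0.5% arm enters the trend test only through p̄.

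- Rising, 10/20/45%: p̄ = 0.25. Overall 15 × 0.065/0.1875 = 5.20; trend 15 × 0.1225/0.375 = 4.90. The trend test keeps nearly all the signal on one degree of freedom.
- Plateau, 10/40/40%: p̄ = 0.30. Overall 15 × 0.06/0.21 = 4.29; trend 15 × 0.09/0.42 = 3.21.
- Reversal, 10/50/40%: p̄ = 0.333. Overall 15 × 0.0867/0.2222 = 5.85; trend 15 × 0.09/0.4444 = 3.04.

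Exact enumeration over all 16³ outcomes:

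| Saline/0.5%/2% | Chi-square | Trend | Change (points) |
|---|---|---|---|
| 10/15/20% | 7.1% | 11.0% | +4 |
| 20/40/60% | 51.9% | 61.2% | +9 |
| 10/20/45% | 52.2% | 63.8% | +12 |
| 5/15/35% | 43.7% | 59.3% | +16 |
| 10/40/40% | 47.4% | 44.3% | −3 |
| 10/50/50% | 71.3% | 64.4% | −7 |
| 20/60/50% | 54.9% | 35.6% | −19 |
| 10/50/40% | 62% | 40% | −22 |

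With equal rates of 10%, 20% or 40% in all arms, both tests reject in 3.5-5.1% of trials.

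**The case against.** The strongest reply is that nothing shows the symptom answers are graded. If they are yes/no, a chi-square is a normal test and a rank test has nothing to gain. This stands: the gap is first a missing scale and only then an order-blind test. A reader might infer that the lost power can be recovered from the same data. That is assured only for the order of the arms; for severity, a graded response may have to be added.

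A reader might also infer that this trial forfeits a known number of points. The documents give no rates, severity levels, effect size or alpha, so every gain quoted here is conditional. An odds ratio of 3-4 is also generous where Hypothesis 2a predicts no change.

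A third tempting reading is that the trend test should replace the overall test for adverse effects. The documents do not support it. Hypothesis 3 asks about a greater rate than control, not a gradient. The Background Summary cites strong virus inactivation in vitro at 0.23%, below both study strengths, and tolerability up to 4.4%. The first is not evidence about nasal irritation, and the second gives no reason to expect a steep rise. The shape is open, and the trend test is weak when the middle arm carries the signal.

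Two further points stand. Kruskal-Wallis also ignores arm order, though it assumes no dose shape in return. With 15 per arm, some expected counts fall below 5 in 88-99% of trials under 10/20/45% and 5/15/35%; this affects the large-sample trend test as much as the chi-square and is a separate matter.

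**Conclusion.** The point holds for severity. Aim 2 names it, no scale is defined, and the only stated test cannot use its order. For graded answers, a rank test had more power than the chi-square in every non-null setting tried: roughly 10-19 points with four levels and an odds ratio of 3-4, about 3 with three levels and an odds ratio of 2. Even after the change, power in the four-level settings is at most about 52%, so these comparisons remain exploratory.

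For adverse effects the case is only for a supplementary trend test. It gains about 4-16 points when rates rise steadily, and loses about 3-7 under a plateau and about 20 under a reversal.

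More power to detect a difference does not establish the absence of one, so Hypotheses 2a and 3 gain no support from the change itself. Time to resolution and the duration of anosmia remain without a suitable analysis. These are secondary and safety outcomes; the primary viral-load comparison is unaffected.

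**What to change.** 1. In Measurements/Outcomes, state that each symptom is rated 0-3 on the existing questionnaires, and name the day whose score is analysed. The documents give Day 3 and Day 5 in one place and daily questionnaires in another.
2. In Statistics, replace the chi-square for symptom severity with a Wilcoxon test (two arms) or Kruskal-Wallis test (three arms), or a proportional-odds model.
3. For adverse effects, keep the overall three-arm comparison, and report the risk difference of each strength against saline with its confidence interval. Add a Cochran-Armitage test with equally spaced scores, labelled as supplementary.
4. Show any claimed power gain as a range with its assumptions, including the plateau and reversal cases.

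The cost is one response option on forms already in use and a few lines of Statistics wording, with no extra subjects, visits or swabs. Because the overall comparison stays, the trend test's weakness under a plateau or reversal takes nothing away from it. The supplement does add one more test per adverse effect, to be read as such.
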